9.1 Discontinuation and completion

9.1.1 Study treatment discontinuation and study discontinuation

This study involves single i.v. infusion of an approximate duration of CCI _____, and therefore the infusion can be interrupted if necessary. In case the clinical setting requires it (e.g. long i.v. line),

Commercially Confidential Information

Discontinuation of study treatment for a participant occurs when study treatment is stopped earlier than the protocol planned duration. Discontinuation of study treatment can be decided by either the participant or the investigator.

Study treatment must be discontinued under the following circumstances:

- Participant/guardian decision - participants may choose to discontinue study treatment for any reason at any time. The investigator believes that continuation would negatively impact the safety of the participant or the risk/benefit ratio of trial participation
- Moderate or severe hypersensitivity reaction occurs, including any of the following: anaphylaxis ([Section 16.1](#)), fever, chills, urticaria, dyspnea, headache, myalgia, hypotension. Immediate discontinuation of study treatment and initiation of appropriate medical treatment is required in such cases.
- Moderate or severe infusion-related reaction to study drug.
- Any protocol deviation or situation that results in a significant risk to the participant's safety.

The appropriate personnel from the site and Novartis will assess whether investigational drug treatment should be discontinued for any participant whose treatment code has been broken inadvertently for any reason.

If discontinuation of study treatment occurs, investigator must determine the primary reason for the participant's premature discontinuation of study treatment and record this information on the Dosage Administration CRF.

Participants who discontinue study treatment or who decide they do not wish to participate in the study further should NOT be considered withdrawn from the study UNLESS they withdraw their consent (see 'Withdrawal of Informed Consent' [Section 9.1.2](#)). Where possible, they should return for the assessments indicated in the Assessment Schedule. If they fail to return for these assessments for unknown reasons, every effort (e.g., telephone, e-mail, and letter) should be made to contact the participant/pre-designated contact as specified in 'Lost to follow-up' [Section 9.1.3](#). This contact should preferably be done according to the study visit schedule.

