9.1.2 Withdrawal of informed consent

Participants may voluntarily withdraw consent to participate in the study for any reason at any time. Withdrawal of consent occurs only when a participant:

- Does not want to participate in the study anymore,
and
- Does not want any further visits or assessments
and
- Does not want any further study related contacts

In this situation, the investigator should make a reasonable effort (e.g. telephone, e-mail, letter) to understand the primary reason for the participant's decision to withdraw his/her consent and record this information.

Where consent to the use of personal and coded data is not required, participant therefore cannot withdraw consent. They still retain the right to object to the further use of personal data.

Study treatment must be discontinued and no further assessments conducted, and the data that would have been collected at subsequent visits will be considered missing.

Further attempts to contact the participant are not allowed unless safety findings require communicating or follow-up.

All efforts should be made to complete the assessments prior to study discontinuation. A final evaluation at the time of the participant's study discontinuation should be made as detailed in the assessment table.

Novartis/Sponsor will continue to retain and use all research results (data) that have already been collected for the study evaluation.

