6.2 Secondary objectives

6.2.1 Variables

The following variables and corresponding objectives are classified as secondary pharmacodynamic endpoints and will be evaluated for their effect of MAS825 compared with placebo,

- On inflammatory status: Serum C-reactive protein (CRP) levels and ferritin
- On clinical status: Endpoints based on the 9-point ordinal scale:
- Survival without the need for invasive mechanical ventilation at Days 15 and 29 defined by a 9-point ordinal scale score of < 6 points at all time points
- At least one level improvement in clinical status at Days 15 and 29: defined as difference of ≥ 1 in the 9-point ordinal scale score of the screening value – Day 15 or Day 29 respectively.
- Clinical status over time

Missing data

For the clinical status 9-point ordinal scale missing values will be handled as follows:

- For participants who died prior to Day 29: The score for death will be imputed for all visits following the death up to and including Day 29.

For all other participants: LOCF will be applied up to and including Day 127. Following discharge or early discharge LOCF will be applied to all intermediate visits.

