6.2.2 Descriptive analyses

CRP and ferritin

Panels of individual spaghetti plots over time for CRP and ferritin will be provided using a logscale. The profiles of all participants in the respective treatment group will be included in these graphs as grey lines in the background and the respective individual participants profile will be plotted with darker color in the foreground. The respective applicable normal ranges will be added and it will be indicated by a symbol if a patient died.

Survival without the need for invasive mechanical ventilation

The numbers and percentages of responders will be calculated up to Day 15 and up to Day 29 respectively. It will be presented by treatment group together with the difference in response rates.

Improvement in clinical status

The numbers and percentages of responders will be calculated up to Day 15 and up to Day 29 respectively. It will be presented by treatment group together with the difference in response rates and a two-sided 90% CI based on Fishers exact test.

In addition a shift table of changes in response status will be provided with weekly time intervals (e.g. baseline, week 1, week 2, week 3 and week 4). For this the following response categories will be included:

- improvement of at least 1 step from baseline,
- no change from baseline
- worsening from baseline.

Also a stacked barchart illustrating the percentage of participants in each response categories as outlined above will be provided. Treatment groups will be presented next to each other. This will be provided for weeks 1, 2, 3 and 4.

For the subgroup analysis a shift table and stacked barchart for subgroup of participants with high baseline CRP by high and low corticosteroid dose during week 1 will be provided.

Clinical status over time

The 9-point ordinal scale will be summarized (mean, median, standard deviation, minimum, maximum, frequencies and percentages in each category) will be summarized by visit (including a time point for data from early discharge) and treatment group.

A stacked barchart illustrating the percentage of participants for each category of the 9-point ordinal scale with one bar will be provided. Treatment groups will be presented next to each other within one category. This will be provided for Day 8, Day 15, Day 21 and Day 29 (labeled as weeks 1, 2, 3 and 4).

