6.2.5 Graphical presentation of results

CRP and ferritin

Estimated mean CRP +/- SE will be plotted over time by treatment group. The estimated geometric mean ratio to baseline in CRP +/- SE will also be presented. Ferritin levels will also be presented in the same manner.

For the subgroup analyses the following graphs will be provided:

- A line plot of the geometric means (+/-SE) are provided by corticosteroid dose category and treatment group together with the estimated values of the primary analyses by treatment group over time.

Side-by-side a second line plot on the treatment ratios (90% CI) per by corticosteroid dose category together with the estimated treatment difference (90% CI) of the primary analyses over time is given.

Survival without the need for invasive mechanical ventilation

Kaplan-Meier graphs with separate lines by treatment group will be provided for a graphical presentation. Participants will be censored discontinuing from the study or not experiencing an event.

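### Last-score carry-forward has no exception for leaving the study, so participants of unknown status count as Day 15 and Day 29 survivors free of invasive ventilation, while the Kaplan-Meier graph censors them

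*SAP*

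**What the plan says.** SAP 6.2.1 derives survival free of invasive ventilation from the 9-point scale. Success at Days 15 and 29 is "defined by a 9-point ordinal scale score of < 6 points at all time points". The missing-data paragraph covers the whole scale ("For the clinical status 9-point ordinal scale missing values will be handled as follows") and has two branches:

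- Known deaths before Day 29: "The score for death will be imputed for all visits following the death up to and including Day 29".
- Everyone else: "For all other participants: LOCF will be applied up to and including Day 127". A further sentence extends this to the visits skipped after discharge.

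Neither branch mentions withdrawal of consent or loss to follow-up.

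SAP 6.2.2 then summarises the endpoint: "The numbers and percentages of responders will be calculated up to Day 15 and up to Day 29 respectively", by treatment group and with the difference in rates. It plans a 90% confidence interval for the improvement endpoint but not for this one.

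SAP 6.2.5 plans Kaplan-Meier curves of the same endpoint: "Participants will be censored discontinuing from the study or not experiencing an event".

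**The concern.** A participant who leaves on Day 4 with score 5 has that score carried 25 days to Day 29 and is reported as a success, although nothing is known after Day 4. The graph of the same endpoint treats that person as unknown from the day of leaving. The SAP does not say which display governs.

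The default is one-sided. Protocol 5.2 (criterion 4) excludes patients intubated before randomization, so participants enter below score 6. Anyone who exits before a recorded event becomes a success, even with only a baseline score.

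The SAP is stricter for APACHE II. Section 6.1.7 caps carry-forward at 4 days for most components and imputes only where at least one component was reported at that visit. The ordinal scale has neither safeguard.

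At stake are the size of a named secondary endpoint's response rates and the between-arm difference when leavers are unbalanced. The response table would not show how many of its successes were imputed.

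**Working it through.** The plan states no rate, power or sample size for this endpoint, so there is no figure of its own to reproduce. The check is a rule trace followed by arithmetic on stated assumptions.

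**Inputs.** From the documents: the SAP 6.2.1, 6.2.2 and 6.2.5 rules above, and 60 participants per arm (Protocol 12.9.1). Assumed, because the documents give no value: the fraction w leaving alive and event-free with no later contact, their true Day 29 success probability s, and the overall event-free rate S.

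**Step 1, rule trace.** Take a participant with score 4 on Day 6 who then withdraws consent.

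| Display | Rule | Result |
|---|---|---|
| Response table (6.2.1, 6.2.2) | score 4 carried to Days 15 and 29 | success at both |
| Kaplan-Meier graph (6.2.5) | censored on leaving | unknown afterwards |

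**Step 2, size per arm.** Leavers truly contribute w·s to the arm's success rate. Carry-forward credits them with w. The excess is w(1-s).

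| w | s = 0.6 | s = 0.7 | s = 0.8 |
|---|---|---|---|
| 5% | 2.0 points | 1.5 | 1.0 |
| 10% | 4.0 | 3.0 | 2.0 |

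Each leaver whose true outcome was failure adds 1/60 = 1.7 points. If 10% leave one arm and 3% the other, with the same s, the difference shifts by 0.07(1-s), which is 1.4 to 2.8 points for s from 0.8 down to 0.6.

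**Step 3, the displays side by side.** Suppose 6 of 60 leave event-free before any of 12 later events among the other 54:

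- carry-forward: (42 + 6)/60 = 80.0%
- Kaplan-Meier: 42/54 = 77.8%
- leavers as non-responders: 42/60 = 70.0%

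Now assume a constant hazard over 28 days and m leavers whose exit is unrelated to outcome. The excess of carry-forward over Kaplan-Meier is (m/60)(1 - S/S_t), where S_t is the event-free rate at exit. With S = 0.70 and 6 leavers at Day 5, S_t = 0.70^(4/28) = 0.950 and S/S_t = 0.737. The excess is 0.10 × 0.263 = 2.6 points: 72.6% against 70.0%, and 62.6% with leavers as non-responders. Over S of 0.6-0.8, 3 to 9 leavers, and exit at Day 5 or 15, the excess runs from 0.5 to 5.3 points.

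**Step 4, bounds.** Moving all leavers from success to failure shifts an arm by m/60: 5, 10 or 15 points for 3, 6 or 9 leavers. With 0 leavers against 6, or 3 against 9, the between-arm difference moves by 6/60 = 10 points.

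**Step 5, scale.** At an assumed 70% success in both arms, the standard error of the difference is √(2 × 0.7 × 0.3/60) = 8.4 points, and the 90% half-width is 1.645 × 8.4 ≈ 14 points.

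**The case against.** The strongest reply is that these are two displays with two purposes. A proportion needs some imputation rule, a survival curve normally censors at last follow-up, and both can be programmed as written. That stands: the two rules give different answers for the same people, but they do not make the SAP unworkable.

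The affected group is also narrow. Stopping treatment is not leaving: such participants "should NOT be considered withdrawn from the study UNLESS they withdraw their consent". Protocol 8.3.3 and Table 8-1 provide phone assessments after discharge, so carrying a score across those planned gaps is reasonable. Protocol section 8 asks for the Day 15 assessments when someone leaves before Day 15, but these describe status at exit, not at Day 15. What remains is participants with no later contact. If they were mostly well, s is near 1 and the excess nearly vanishes.

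A reader might infer that Kaplan-Meier should replace the proportion. The case for that is not clear, because censoring is also biased when exit is related to outcome. Suppose 10% leave before any event and stayers succeed at 70%. Carry-forward gives 0.63 + 0.10 = 73.0% and Kaplan-Meier 70.0%. The truth is 0.63 + 0.10s: 69.0% at s = 0.60, where Kaplan-Meier is closer, but 72.5% at s = 0.95, where carry-forward is closer. The errors are equal when 1 - s = s - 0.70, at s = 0.85.

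A reader might also infer a conflict with Protocol 9.1.2, which says of withdrawn consent that "the data that would have been collected at subsequent visits will be considered missing". Calling data missing does not forbid imputing them, and the sentence does not expressly cover loss to follow-up.

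Finally, the heat map in SAP 6.2.2 marks imputed values and SAP 7.2.1 tabulates discontinuations by reason. Neither shows how many responders in the table were imputed. SAP 6.3 is redacted, so further analyses cannot be ruled out.

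**Conclusion.** The point holds as a modest one. Followed as written, SAP 6.2.1 and 6.2.2 count no-contact leavers last seen below score 6, with no earlier event, as Day 15 and Day 29 successes. The rate is overstated whenever their true success probability is below 100%. The size is w(1-s), or 1 to 4 points per arm under the assumed 5-10% leaving and s of 0.6-0.8. It could be close to zero, and the documents cannot settle where it lies.

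Two stronger readings are not supported. Nothing in the documents says that exit happens mainly during deterioration; the overstatement needs only s below 1. Nor is it shown that the table and the curve would point in opposite directions. A shift of 1.4 to 2.8 points is small against a standard error of about 8.4, so a sign change would need a difference already near zero.

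For improvement by at least one level, carry-forward fixes status at exit and the bias can go either way. The primary APACHE II analysis is unaffected, and no test is planned for this endpoint in SAP 6.2.2.

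**What to change.** In SAP 6.2.1 and 6.2.2, for the responder endpoints:

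1. Limit carry-forward to visits missed between two observed scores, and to visits omitted after discharge where a later contact confirms status.
2. Do not count participants who discontinued with unknown Day 15 or Day 29 status as observed successes. Report their number by arm and state the denominator of the main percentage.
3. Add one sensitivity table counting them as non-responders.
4. Show the Day 15 and Day 29 estimates from the Kaplan-Meier curves already planned in 6.2.5 alongside the proportions, not in their place.

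The cost is a few sentences and one table, with no new data collection. The non-responder analysis is conservative and may understate success if leavers were well, so it should be read as a bound.

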Pregnancy test – urine/serum (local lab) ⁹	X									X			X
Blood chemistry including CRP, Ferritin, LDH, ANC, D-dimer, troponin and BNP (local lab) ⁸	X	X	X	X	X	X	X	X	X	X	X	X	X
Hematology (local lab) ⁸	X	X	X	X	X	X	X	X	X	X	X	X	X
Coagulation Panel ⁸	X	X	X	X	X	X	X	X	X	X	X	X	X

Commercially Confidential Information

Drug administration record ¹¹	X												
Concomitant medications/Therapies including inotropic support										X			
Adverse events/serious adverse events										X			
Safety Follow up Call										X		X	X
Study completion information													X

X = assessment to be recorded in the clinical database or received electronically from a vendor
S = assessment to be recorded in the source documentation only

1. Informed consent must be signed prior to any study-related procedure.
2. Study treatment may start immediately after obtaining the screening/baseline measurements and confirming eligibility. Day 15 visit should be performed for all patients.
3. If patient is discharged prior to Day 15 (early discharge), then assessments on the day of discharge should be performed according to the schedule listed under Day 15 and patient should return to the site for the Day 15 assessment, with a time window of +2 days (if hospital visit is not possible, then home nursing is allowed on day 15 (with a time window of +2 days) that should include all possible assessments including oxygen saturation with portable monitors). In case, home nursing is not possible, patients will be contacted by phone on day 15 (with a time window of +2 days), where respiratory history, performance status, adverse events, concomitant medication and medical and surgical history will be obtained). No time window for Day 15 is allowed if the patient is not discharged prior to day 15.

Commercially Confidential Information

Period	Screening / Baseline / Treatment	Treatment ²								Post-Treatment Follow-up			EOS
Visit Name	Screening / Baseline / Treatment ¹⁴	Observation								Discharge ³	Follow-up ⁴ (if hospitalized assessments performed at site every 2 days; if discharged only telephone call on Day 29)	Safety follow-up ⁴	EOS/Safety Follow up ⁴
Days	-1 to 1	2	4	6	8	10	12	14	15	17, 19, 21, 23, 25, 27	29 (-1/+3 days)	45 ⁵ (+/-7 days)	127 (+/-7 days) ⁵

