4.	f patient is discharged after Day 15 and prior to Day 127 (discharge), then assessments on the day of discharge should be performed according to the schedule listed under Day 127. Furthermore, visits at Days 29, 45 and 127 should be conducted via phone for patients who were discharged prior to the visit (see footnote 3 for assessments to be obtained on the phone). Visits between day of discharge and Day 127 can be omitted. If the patient remains hospitalized, however, all assessments noted in the table should be conducted on the visit day noted.												
5.	Results confirming positive SARS-CoV-2 virus by PCR or by other approved diagnostic methodology available within 7 days and chest X-ray, CT or MRI scan within 5 days prior to randomization may be used for eligibility.												
6.	Vital signs include heart rate, respiratory rate (if not on mechanical ventilation), systolic and diastolic blood pressure and body temperature. If possible, vital signs should be recorded at the same time at every visit for a patient (i.e. morning, afternoon or evening) and upon significant clinical changes. Oxygen saturation (if not on mechanical ventilation) or PaO ₂ /FiO ₂ should be measured at the same time as the vital signs measurements. If patient is receiving supplemental oxygen (not on invasive ventilation) then oxygen flow rate and/or FiO ₂ and oxygen saturation to be collected.												
7.	If not possible to measure height, it can be reported by the patient. Height will be measured only at screening/baseline/treatment visit.												
8.	Hematology, blood chemistry and coagulation panel including CRP, Ferritin, LDH, ANC, D-dimer, troponin and BNP should be measured by the local laboratory.												
9.	Pregnancy test applicable only for females of childbearing potential; serum pregnancy test (serum hCG) will be performed by local laboratory. For enrollment a negative urine test is sufficient												
10.	Commercially Confidential Information												
11.	For the treatment day, all assessments should be performed pre-dose.												
12.	Chest X-ray, CT or MRI scan at Day 15 will be performed and reported only if available and performed according to SoC. The same method should be used at Day 15 (or on day of discharge if prior to Day 15) as was used at screening.												

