8.3.3 Clinical status (9-point ordinal scale)

Assessment of clinical status using a 9-point ordinal scale ([WHO 2020](#)) will be recorded at baseline, Day 2 and then every other day until Day 29 for hospitalized patients ([Appendix 2](#)). If a patient is discharged from the hospital, the assessment will be made by phone on the visit dates noted in [Table 8-1](#). Each day, the patient's status from the previous calendar day is reviewed; the ordinal score is assigned based on the patient's worst status from the previous day. This score (based on the review of the previous day) will be recorded (i.e. on Day 3, the Day 2 score is determined from review of all data recorded on Day 2, and the worst score is recorded as the score for Day 2). In addition, on Day 127 or the Day of discharge, clinical status on Day 127 or the Day of discharge should be recorded.

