16.2 Appendix 2: 9-point ordinal scale determination

The ordinal scale is an assessment of the clinical status at the first assessment of a given study day. Each day, the worse score for the previous day will be recorded. i.e. on Day 3, Day 2 score is obtained and recorded as Day 2.

The scale is as follows:

Patient State	Descriptor	Score
Uninfected	No clinical or virological evidence of infection	0
Ambulatory	No limitation of activities	1
	Limitation of activities	2
Hospitalized	Hospitalized, no oxygen therapy	3
Mild disease	Oxygen by mask or nasal prongs	4
Hospitalized Severe disease	Non-invasive ventilation or high-flow oxygen	5
	Intubation and mechanical ventilation	6
	Ventilation + additional organ support - pressors, RRT, ECMO	7
Dead	Death	8

Source: [\(WHO 2020\)](#)

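### Carrying the 9-point score forward after discharge shows some participants at home as hospitalised at Days 8 and 21, and the phone-visit list leaves the Day 29 improvement endpoint open to the same error

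*SAP*

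**What the plan says.** **Imputation.** SAP 6.2.1 imputes the death score at later visits up to Day 29 for participants who die before Day 29. For everyone else: "For all other participants: LOCF will be applied up to and including Day 127". It then adds: "Following discharge or early discharge LOCF will be applied to all intermediate visits". No rule gives an ambulatory score to a visit skipped after discharge.

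**Scoring a day.** Protocol 8.3.3 assigns each day the participant's worst status on that day. Appendix 2 says: "The ordinal scale is an assessment of the clinical status at the first assessment of a given study day", and then also describes recording the worse score of the previous day. Section 8.3.3 further asks for clinical status on the day of discharge, without saying whether this means before or after leaving.

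**Collection after discharge.** Protocol 8.3.3, referring to Table 8-1: "If a patient is discharged from the hospital, the assessment will be made by phone on the visit dates noted in". Footnote 3 of that table describes Day 15 after an early discharge: "patient should return to the site for the Day 15 assessment, with a time window of +2 days". Home nursing is the second choice and a phone call the last. It describes the call as one "where respiratory history, performance status, adverse events, concomitant medication and medical and surgical history will be obtained". For the later visits (Days 29, 45 and 127), footnote 4 says that they "should be conducted via phone for patients who were discharged prior to the visit (see footnote 3 for assessments to be obtained on the phone". The 9-point scale is not among the items listed. Protocol section 3 allows the other visits between discharge and Day 15, or between discharge and Day 29, to be omitted.

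**Display.** SAP 6.2.2 plans by-visit summaries, weekly shift tables, a heat map and stacked bar charts. Of the category bar chart it says: "This will be provided for Day 8, Day 15, Day 21 and Day 29 (labeled as weeks 1, 2, 3 and 4").

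**The concern.** Discharge alive is itself information about the score. The participant is out of hospital and, on this scale, belongs at 0, 1 or 2. Carrying the discharge-day score forward replaces that information with a contrary value. The SAP treats death as a known state and fills it in, but does not do the same for discharge.

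Two secondary endpoints are involved: clinical status over time, and at least one level of improvement at Days 15 and 29. If MAS825 brought discharge forward, the weekly displays would hide part of that benefit, because a participant discharged on Day 5 looks the same at week 1 as one still in the ward with the same score. If the scale is also missed at the Day 29 call, the same value reaches an endpoint day.

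**Working it through.** There is no stated figure to reproduce, so the check traces which day supplies the score at each reported day.

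**Step 1: the discharge-day score.** In the scale (Protocol Appendix 2, SAP 10.6), hospitalised states are 3 to 7 and living participants outside hospital are 0 to 2. A participant is in hospital for part of the discharge day and at its first assessment. The worst-status rule and the first-assessment rule therefore both give 3 or more. Only the additional discharge-day record in 8.3.3 could be read as status after leaving, and neither document says which record LOCF would carry.

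**Step 2: where the score at each reported day comes from.** For each discharge day from 3 to 28, take the last day with a score on or before the reported day. In-hospital visits and the discharge day are always scored. Three readings differ in what is scored after discharge. The entries are the discharge days whose discharge-day score is carried to the reported day.

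| Reading | Day 8 | Day 15 | Day 21 | Day 29 |
|---|---|---|---|---|
| A: 8.3.3 followed, Days 15 and 29 scored | 3-7 | none | 15-20 | none |
| B: Day 15 scored at site or home, Day 29 call without the scale | 3-7 | none | 15-20 | 15-28 |
| C: Day 15 also by phone, without the scale | 3-7 | 3-14 | 3-20 | 3-28 |

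Under A and B, a participant discharged before Day 15 carries the at-home Day 15 score, not the discharge-day score, to Day 21. The other omitted visits in the by-visit summaries follow the same logic.

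**Step 3: effect on one-level improvement.** Improvement means screening score minus later score of at least 1. Participants are hospitalised and not intubated at entry, so the screening score is taken as 3, 4 or 5.

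| Screening | Carried 3 | Carried 4 | Carried 5 | At home, score 2 |
|---|---|---|---|---|
| 3 | no | no | no | yes (3 - 2 = 1) |
| 4 | yes | no | no | yes (4 - 2 = 2) |
| 5 | yes | yes | no | yes (5 - 2 = 3) |

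The responder status is wrong only where the carried score is not below screening. Example under reading B: screening 4, discharged on Day 18 after needing nasal oxygen that day, so the discharge-day score is 4. The Day 29 call does not take the scale, 4 is carried, and 4 - 4 = 0. The participant is a non-responder after 29 - 18 = 11 days at home.

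**Step 4: effect on survival without invasive ventilation.** This requires a score below 6 at all time points. A carried 3, 4 or 5 satisfies it just as an at-home score would.

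**The case against.** The strongest reply is that the protocol does require the scale after discharge. Section 8.3.3 says so, and the Table 8-1 grid marks the scale at the follow-up visits. Footnote 3 is a general list that never says the scale is dropped, and it includes items from which an ambulatory score could be judged. At Day 15 the phone is the last resort. On this view the SAP sentence concerns only visits between recorded ones, and the endpoint days are observed.

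Much of this stands. A reader might infer that discharged participants in general are analysed as hospitalised on Days 15 and 29, or that week 3 is wrong for nearly everyone discharged earlier. The documents do not support either: reading A leaves both endpoint days untouched, and week 3 is then affected only for discharge on Days 15 to 20. Nor do they support a figure for how far a treatment difference in improvement would shrink. That needs the discharge rates, the share without a post-discharge score and the share whose carried score is not below screening, and none is given.

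The reply does not remove two things. Reading A, the most favourable to the plan, still misplaces participants at weeks 1 and 3. And the grid marks cannot settle what a call collects, because the same columns are marked for blood chemistry and haematology.

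The displays are descriptive, the heat map stripes LOCF values and flags discharge, and disposition tables count discharges before Days 15 and 29. These soften the problem, but the SAP specifies no such marking for the bar charts, shift tables or by-visit summaries.

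A last objection is that capping the score at 2 imposes a favourable value where status is unknown, for example in someone sent home on oxygen. However, 2 is the worst score the scale has for a living person outside hospital.

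**Conclusion.** The point holds in two parts.

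- **Intermediate visits.** As the SAP is written, participants at home are shown as hospitalised at Day 8 if discharged before Day 8, and at Day 21 if discharged on Days 15 to 20, even with full adherence to 8.3.3. This assumes that the carried record is the in-hospital one, as both stated scoring rules imply. It affects the weekly and by-visit displays of clinical status and, where the carried score is not below screening, the weekly improvement categories.
- **Endpoint days.** Section 8.3.3 and footnotes 3 and 4 conflict on whether a call collects the scale. If sites follow the footnotes, Day 29 is exposed for discharge on Days 15 to 28. Day 15, and Day 29 for earlier discharges, are exposed only if the Day 15 contact was also by phone without the scale. A responder is lost only where the carried score is not below screening.

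The primary endpoint is not involved and ventilation-free survival is essentially unaffected. The number of participants affected cannot be derived from the documents.

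**What to change.** 1. **SAP 6.2.1.** For participants discharged alive to the community, set each unrecorded post-discharge visit to the lower of the last score and 2, until the next recorded score, readmission or death. Do not carry a hospital score past the day of discharge.
2. **Table 8-1, footnotes 3 and 4.** Add the 9-point scale to the items obtained by phone, in line with 8.3.3.
3. **Protocol 8.3.3 and Appendix 2.** Reconcile the worst-status and first-assessment wording, and say whether the discharge-day record describes the participant before or after leaving.

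The cost is one SAP sentence, one phone item and one clarified scoring rule. The small downside is that the imputation assumes ambulatory status, so a transfer to another acute facility must not count as discharge.
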